12.0 STUDY OR STUDY SITE TERMINATION

The sponsor has the right to suspend or terminate the study at any time. The study may be suspended or terminated for any reason.

13.0 QUALITY CONTROL AND QUALITY ASSURANCE

The sponsor will implement and maintain quality control and quality assurance procedures with written SOPs to ensure that the study is conducted and data are generated, documented, and reported in compliance with the protocol, Good Clinical Practice (GCP), and applicable regulatory requirements.

All protocol deviations and the reasons for such deviations are to be documented in the source documents and reported to the sponsor.

13.1 Changes to the Protocol

The Investigator may not deviate from the protocol without a formal protocol amendment having been established and approved by an appropriate IRB/independent ethics committee (IEC), except when necessary to eliminate immediate hazards to the subject. Any deviation may result in the subject having to be withdrawn from the study and rendering that subject nonevaluable.

13.2 Monitoring

In accordance with Code of Federal Regulations 21 CFR 312.56, ICH GCP and local regulations, the clinical monitor will periodically inspect all eCRFs, study documents, research facilities, and clinical laboratory facilities associated with this study at mutually convenient times during and after completion of the study. As required by 21 CFR 312 Subpart D (Responsibilities of Sponsors and Investigators), ICH GCP, and local regulations, the monitoring visits provide the sponsor with the opportunity to evaluate the progress of the study; verify the accuracy and completeness of eCRFs; ensure that all protocol requirements, applicable FDA, ICH GCP, and local regulations, and Investigator's obligations are being fulfilled; and resolve any inconsistencies in the study records. This includes inspection of all documents and records that are required to be maintained by the Investigator, including but not limited to medical records (office, clinic, or hospital) for the subjects in this study. The names and identities of all research subjects will be kept in strict confidence and will not appear on eCRFs or other records provided to or retained by the sponsor. The Investigational New Drug Application (IND) regulations also require the Investigator to allow authorized representatives of the sponsor, IRB/IEC, and FDA to inspect and make copies of the same records. The names and identities of the subjects need not be divulged to the sponsor; however, the records must nevertheless be inspected. This can be accomplished by blacking out the subject's name and replacing the name with the subject's study identification number. If these requirements are in conflict with local regulatory restrictions or institutional requirements, the Investigator must inform the sponsor of these restrictions before initiation of the study.

13.3 Direct Access to Source Data/Documents for Audits and Inspections

Members of the sponsor's GCP Quality Assurance Department or designees may conduct an audit of a clinical site at any time during or after completion of the study. The Investigator will be informed if an audit is to take place and advised as to the scope of the audit. Inspections and audits are typically carried out during the clinical and reporting phases of this study to ensure that the study is conducted and data are generated, documented, and reported in compliance with the protocol, GCP, written SOPs and applicable laws, rules, and regulations.

Representatives of the FDA or other regulatory agencies, including IRB/IEC representatives may also conduct an audit of the study. If informed of such an inspection, the Investigator should notify the sponsor immediately. The Investigator will ensure that the auditors have access to the clinical supplies, study site facilities, laboratory and that all data (including original source documentation) and all study files are available, if requested.

14.0 ETHICS

This study will be conducted to be consistent with the principles that have their origin in the Declaration of Helsinki and in accordance with FDA regulations (21 CFR § 11, 50, 54, 56, and 312), with the ICH GCP guidelines (ICH E6), as well as with any and all applicable federal, state and/or local laws and regulations.

14.1 Institutional Review Board/Independent Ethics Committee Approval

Before enrollment of subjects into the study, as required by federal regulations (21 CFR § 56), ICH GCP and local regulations, the current protocol and ICF will be reviewed and approved by an appropriate IRB or IEC. A letter documenting the IRB or IEC approval must be received by the sponsor before the initiation of the study at a clinical site. Amendments to the protocol will be subject to the same requirements as the original protocol.

The Investigator will submit a progress report at least once yearly to the IRB or IEC. However, the frequency of these reports will depend on IRB or IEC requirements. As soon as possible after completion or termination of the study, the Investigator will submit a final report to the IRB or IEC per the IRB or IEC requirements, and in compliance with FDA regulations and ICH GCPs.

The Investigator, the sponsor, or designee shall promptly notify the IRB or IEC of any SAEs, or any other information that may affect the safe use of the study drug during the course of the study, per the IRB or IEC local requirements, and in compliance with FDA regulations and ICH GCPs.

14.2 Written Informed Consent

Written informed consent must be obtained from each subject or subject's legal representative before entering the study. Subjects/legal representatives will be informed of the nature of the study, and the ICF must be presented to each subject/legal representative in the language in which the subject/legal representative is fluent.

Informed consent will be obtained and documented by each subject or subject's legal representative prior to any protocol-specific procedures. Signed ICFs will be retained by the Investigator with the study records. Each subject/legal representative will be given a copy of the signed and dated ICF.

15.0 DATA HANDLING AND RECORD KEEPING

15.1 Data Collection Instruments and Source Documents

15.1.1 Study Records

During the study, the Investigator will maintain adequate records for the study, including a record of potential subjects screened and medical records, and records detailing the progress of the study for each enrolled subject, laboratory reports, eCRFs, signed ICFs, drug accountability records, correspondence with the IRB or IEC and regulatory agencies' AE reports, and information regarding subject discontinuation and completion of the study.

15.1.2 Data Collection Instruments (DCIs)

Data collection instruments (DCIs) (e.g., eCRFs, eCOA, paper forms) will be used in this study. These instruments are used to transmit the information collected during the performance of this study to the sponsor or sponsor's designee and regulatory authorities. The Investigator must review the DCIs for completeness and accuracy and must approve all data, including any changes made. Furthermore, the Investigator retains full responsibility for the appropriateness and accuracy of all data collected in the DCIs.

15.2 Retention of Essential Documents

All records and documents pertaining to the study including, but not limited to, those outlined above (see Section [15.1.1](#)) will be maintained by the Investigator for a period of at least 2 years after FDA approval of the drug or at least 2 years after withdrawal of the IND under which this study was conducted, whichever is longer. To avoid any possible errors, the Investigator will contact the sponsor before transferring or destroying any study records. The Investigator will also promptly notify the sponsor in the event of accidental loss or destruction of any study records.

16.0 PUBLICATION POLICY

All data are the property of the sponsor. However, it is intended that the results of the study will be published and/or presented at scientific meetings. Any formal presentation or publication of data from this study will be considered as a joint publication by the Investigator(s) and appropriate sponsor personnel. Authorship will be determined by mutual agreement.

The sponsor must receive copies of any intended communication in advance of submission for publication (at least 14 days for an abstract or oral presentation and 30 days for a journal submission). The sponsor will review the communications for accuracy (thus avoiding potential discrepancies with submissions to health authorities), verify that confidential information is not being inadvertently divulged, and provide any relevant supplementary information.

The Investigator may be required to sign the clinical study report if it is to be used in a registration submission to the health authorities of some countries.

18.0 APPENDICES

Not applicable.

BID	twice daily
BMI	body mass index
BP	blood pressure
mBPI-SF	Modified Brief Pain Inventory-Short Form
CI	confidence interval
CLBP	chronic low back pain
COWS	Clinical Opiate Withdrawal Scale
CRO	clinical research organization
C-SSRS	Columbia-Suicide Severity Rating Scale
CYP3A	cytochrome P 450 enzyme isoform 3A
ECG	electrocardiogram
eCRF	electronic case report form
eC-SSRS	electronic Columbia-Suicide Severity Rating Scale
ET	early termination
GCP	Good Clinical Practice
GGT	gamma-glutamyl transferase
GSP	Good Statistical Practice
ICF	informed consent form
ICH	International Conference on Harmonisation
IXRS	Interactive Voice and Web Response System
MADDERS™	Misuse, Abuse, and Divergent Drug Event Reporting System
MedDRA	Medical Dictionary for Regulatory Activities

Abbreviation or Term	Definition
MMRM	mixed model repeated measures
NSAID	non-steroidal anti-inflammatory drug
NRS	Numeric Rating Scale
PHQ-8	Personal Health Questionnaire Depression Scale
PK	pharmacokinetic
QTcF	corrected QT interval, Fridericia's correction
RR	respiratory rate
SAP	statistical analysis plan
SOC	system organ class
SOWS	Subjective Opiate Withdrawal Scale
TBL	total bilirubin
TEAE	treatment-emergent adverse event
ULN	upper limit of normal
US	United States
WHO	World Health Organization

1.0 ADMINISTRATIVE STRUCTURE

This study is being conducted under the sponsorship of Nektar Therapeutics. Statistical analyses will be performed by the Biometrics Department at Nektar Therapeutics and a contract research organization (CRO). Pharmacokinetic (PK) concentrations will be analyzed by Nektar India. Central clinical laboratories and central electrocardiograms (ECGs) are used for processing of laboratory safety specimens and ECG data. The Interactive Voice and Web Response System (IXRS) provider will manage the study drug distribution and inventory management.

2.0 INTRODUCTION

This document is a description of the planned statistical analyses of the data captured according to Nektar Therapeutics Protocol 14-181-08, “A Phase 3 Multicenter, Open-Label, 52-Week Study to Evaluate the Long-Term Safety and Tolerability of NKTR-181 in Subjects with Moderate to Severe Chronic Low Back Pain or Chronic Noncancer Pain”.

This Phase 3 study will be conducted in accordance with the protocol, Good Clinical Practice (GCP), Good Statistical Practice (GSP), and all applicable regulatory requirements.

Analyses of pharmacokinetics will be addressed in a separate analysis plan.

3.0 STUDY OBJECTIVES

3.1 Primary Objective

The primary objective of the study is to evaluate the long-term safety and tolerability of NKTR-181 in subjects with moderate to severe chronic low back pain or chronic noncancer pain.

3.2 Secondary Objectives

The secondary objective is to evaluate the effectiveness of NKTR-181 as measured by the modified Brief Pain Inventory-Short Form (mBPI-SF).

4.0 STUDY DESIGN

This is a multicenter, Phase 3, open-label safety and tolerability study in which approximately 600 subjects will receive open-label NKTR-181 for up to 12 months (52 weeks) from approximately 100 sites. Subjects may include newly enrolled subjects (approximately 250 De Novo Subjects) and subjects who have recently completed Study 14-181-07 or Study 14-181-12 (Rollover Subjects).

The study comprises 3 periods:

- **Screening:** Up to 21 days; Visits 1-2
- **Treatment:** 52 weeks; Visits 3-22
- **Safety Follow-Up:** Approximately 14 days after the last dose of study drug; Visits 23-24

This study will also investigate the PK of NKTR-181 in patients with chronic low back pain or chronic noncancer pain. Blood samples for PK analyses will be collected from all subjects according the Schedule of Assessments (Section 1.2 of protocol), and during a complete 12-hour dosing interval in a substudy of approximately 100 subjects at selected sites.

The three study periods are described in further detail in Study Protocol 14-181-08, Sections 6.1 to 6.3. A schematic of the study design is presented in Section 1.1, and the Schedule of Assessments is presented in Section 1.2 of the protocol.

4.1 Method of Randomization

Randomization is not applicable to this study.

5.0 STUDY ENDPOINTS

Key Safety Endpoint:

- Incidence, type, seriousness, and severity of adverse events (AEs) reported
- Clinical laboratory evaluations
- Electrocardiograms (ECGs)
- Vital signs (respiratory rate, pulse, heart rate, blood pressure, and temperature)
- Drug withdrawal as measured by the Clinical Opiate Withdrawal Scale (COWS) and the Subjective Opiate Withdrawal Scale (SOWS)
- Incidence of aberrant drug behavior according to MADDERS™ assessment
- Suicidality assessment (Columbia-Suicide Severity Rating Scale [C-SSRS]).

Efficacy Endpoints:

- • The mBPI-SF assessed at clinic visits.

6.0 ASSESSMENTS

6.1 Efficacy Assessments

6.1.1 Modified Brief Pain Inventory-Short Form (mBPI-SF)

The mBPI-SF ([Mendoza, 2006](#)) was developed to provide information on pain intensity and the degree to which pain interferes with patient functioning. Using a 0 to 10 numerical rating scale (NRS), subjects rate their pain at the time of responding to the questionnaire (Pain Now), and also at its worst, least, and average over the previous 24 hours. With 0 being "no interference" and 10 being "interferes completely," the mBPI-SF asks for ratings of the degree to which pain interferes with mood, walking and other physical activity, work, social activity, relations with others, and sleep.

6.2 Safety Assessments

Safety assessments include adverse events and serious adverse events, clinical laboratory tests, vital signs, twelve-lead ECGs, relevant and significant medication history (including history of substance or opioid abuse, medical/surgical history, and concurrent illnesses), pregnancy tests, drug and alcohol screening, Columbia-Suicide Severity Rating Scale (C-SSRS) suicidality assessment, Clinical Opiate Withdrawal Scale (COWS; [Wesson, 2003](#)), Subjective Opiate Withdrawal Scale (SOWS; [Handelsman, 1987](#)), and Misuse, Abuse, and Divergent Drug Event Reporting System (MADDERS™).

7.0 STATISTICAL CONSIDERATIONS

Statistical analysis of this study will be the responsibility of Nektar Therapeutics or its designee using the SAS® software version 9.4 or greater. Other analyses than those stated in the statistical analysis plan might be performed to gain information needed for the planning and analyses of future studies.

7.1 General Considerations

Generally, if not specified, continuous data will be summarized by descriptive statistics (n, mean, standard deviation, median, minimum, maximum). Categorical data will be summarized by the number and percentage of subjects. All assessments, if necessary, will be summarized by Denovo naive, Denovo opioid experienced, Rollover by treatment received in feeder study. All statistical tests, as deemed necessary, will be 2-sided with a significance level of 5%.

7.2 Study Day

- The day of the titration start (Visit 3 date) will be called Titration Day 1. Visit 10 is the end of titration, the dose at visit 10 is defined as stable dose. The day of the stable dose (Visit 10 date) will be called Day I. Study day will be calculated from the Day 1.
- Baseline is defined as the last non-missing observation prior to or on Titration Day 1. Change from baseline variables will be calculated as the post-baseline value minus baseline value.

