3. Demographics include birth date, race/ethnicity, smoking status, height, weight, BMI, and sex at birth. For Rollover Subjects, all demographic information (except weight and BMI) will be carried forward from Study 14-181-07 or Study 14-181-12.
4. The Personal Health Questionnaire Depression Scale (PHQ-8) is a self-administered (i.e., the subject completes the scale) version of the Primary Care Evaluation of Mental Disorders for mood. Subjects who score 10 or greater are not eligible to participate in this study.
5. Medical history includes medication history, history of substance or opioid abuse, medical/surgical history and concurrent illnesses and will be collected for all subjects and noted as to whether the condition is active. All relevant medical history will be collected and carried forward for Rollover Subjects. Ongoing adverse events that occurred in Study 14-181-07 and Study 14-181-12 will continue to be followed for Rollover Subjects.
6. Subjects who have a positive alcohol breath test will not be eligible for participation in this study.
7. Physical examination, including all major organ systems (general, head, eyes, ears, mouth/throat, neck, heart, lungs, abdomen, lymph nodes, joints, extremities, integumentary, neurologic, and psychiatric) will be performed for all De Novo Subjects. Physical examinations will not be conducted on Rollover Subjects.
8. Vital signs (respiratory rate, blood pressure, pulse, and temperature) will be measured after subjects have been resting for at least 5 minutes.
9. Subjects must be resting quietly in the supine position for > 5 minutes prior to collection of 12-lead ECG. During the treatment period, if an ECG is obtained and reveals that the subject's QTcF interval is > 500 msec or has an increase of ≥ 60 msec compared to baseline QTcF and confirmed with a second ECG within 30 minutes, treatment with study medication should be interrupted. In the event this occurs, the investigator should contact the Medical Monitor as soon as possible to discuss if the subject can continue on treatment or if the subject should stop study medication. Subjects who are discontinued will be required to complete the ET Visit and all safety follow-up procedures.

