5.1.1 Rollover Subjects

Rollover Subjects must also meet the following criteria in order to be eligible for the study:

1. Must fully complete through the End of Treatment Visit of Study 14-181-07 or Study 14-181-12 prior to receiving study drug.

2. Have no break in treatment with study drug.

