6.0 TREATMENT PLAN

6.1 Screening Period (Visits 1-2)

Subjects will provide written informed consent to participate in the study before completing any protocol-specified procedures or evaluations. Subjects will be eligible to enter the Screening Period in 2 ways:

- If they are currently enrolled in and expected to complete Study 14-181-07 or Study 14-181-12 through the End of Treatment Visit.; these subjects (either on NKTR-181 or placebo) may be eligible to enroll in this study as a **Rollover Subject**
- If they have a clinical diagnosis of moderate to severe chronic low back pain for > 3 months, and are non-tolerant to opioid analgesics (i.e., currently taking no less than 10 mg but no more than 60 mg MSE/day for at least the 7 days prior to signing the ICF); such subjects may be eligible to enroll in this study as a **De Novo Subject**

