6.1.1 Rollover Subjects

Rollover Subjects should have no break in treatment with study drug. Visit 1 (Screening) will take place concurrently with a scheduled, on treatment clinic visit, during Study 14-181-07 and Study 14-181-12.

The End of Treatment Visit in Study 14-181-07 and Study 14-181-12, where the subject has completed tapering to the 100-mg NKTR-181 BID starting dose for this study, will be the first visit of the Treatment Period (Visit 3). There is no Visit 2 for Rollover Subjects.

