8.6 Efficacy Endpoint

The mBPI-SF will be assessed at each visit during the study. The mean of the 4 intensity items (3-6) will be calculated and used as a measure of pain severity. The mean of the 7 interference items (9A-9G) will be calculated and used as a measure of Pain interference. Change from baseline to each month (visit) will be calculated for the Pain severity, Pain interference, and each individual score, if applicable.

If there are missing items when the pain severity score and pain interference score are calculated, the mean of the completed items in one dimension (dimensions include pain severity and pain interference) will be imputed to substitute the missing item, provided that more than 50% of the items in one dimension are completed ([Halling, 1999](#)).

The change from baseline and value for mBPI-SF dimensions and individual scores at each visit will be summarized descriptively over time.

In addition, an exploratory analysis will be performed on mBPI. The change from baseline to the end of the long term safety study will be analyzed. Baseline will be considered as last non-missing assessment on or prior to the first dose in this long term safety study (visit 3). The change from baseline will be analyzed using Mixed Model Repeated Measure (MMRM) analysis. The model will include change from baseline as dependent variable, baseline score as a covariate, subject's status (De Novo or Rollover with NKTR-181 or Rollover with Placebo), time, subject's status and time interaction as fixed effects. Point estimates on the Least Squared means over time will be calculated with corresponding 95% confidence intervals different dose levels. These analysis will be applied to both pain intensity and interference based on mBPI. The pain intensity means and LSmeans over time will be present graphically.

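### For Rollover Subjects coming from NKTR-181, change from baseline leaves out whatever drug effect is already present at baseline

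*SAP*

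**What the plan says.** SAP 7.2 states that "Baseline is defined as the last non-missing observation prior to or on Titration Day 1" and that "The day of the titration start (Visit 3 date) will be called Titration Day 1". SAP Table 1 gives the same cut-off, the first dose date, for every assessment. SAP 8.6 (the mBPI-SF mixed model) and 8.6.1 (responder rates) also refer back to Visit 3. None of these sections has a separate rule for Rollover Subjects.

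Protocol 6.1 says of subjects in the two feeder studies that "these subjects (either on NKTR-181 or placebo) may be eligible to enroll in this study". Protocol 5.1.1 requires that they "Have no break in treatment with study drug". Protocol 6.1.1 adds that "Visit 1 (Screening) will take place concurrently with a scheduled, on treatment clinic visit". It also makes the feeder End of Treatment visit, reached after a taper to 100 mg BID, serve as Visit 3.

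On presentation, SAP 7.1 offers a split by feeder treatment only where judged necessary. SAP 8.7.6 summarizes vital signs and ECGs by titrated dose level. Protocol 11.1 and 11.9 call for De Novo, Rollover and all subjects combined.

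**The concern.** A change score shows a drug effect only if the reference value was taken without the drug. For a Rollover Subject who was on NKTR-181, both values are on drug, so an effect that is already established cancels in part or almost wholly.

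ECG, laboratory and vital-sign results are key safety endpoints under the primary objective, and mBPI-SF is the secondary objective. The error runs toward no change, which for safety measures is the reassuring direction. It also carries into shift tables, the QTc change categories in the SAP appendix (more than 30 and more than 60 ms) and the responder rates.

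The documents supply no pre-drug value elsewhere. Protocol footnotes 3 and 5 carry forward demographics and medical history from the feeder studies, but no measurements. The only cross-study pooling they describe is for population PK and exposure-response.

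**Working it through.** The plan states no figure on this point, so there is none to reproduce. The check traces the baseline visit and then illustrates its size.

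**1. Which visit supplies the baseline** (Protocol 1.2 schedule and footnote 10; status is for a Rollover from NKTR-181)

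| Measure | Last scheduled value on or before Visit 3 | Status at that visit | What the change score loses |
|---|---|---|---|
| QTcF | Visit 1 (none at Visit 3, next at Visit 10) | on feeder treatment | nearly all of a constant effect if the later dose is similar |
| Hematology, urinalysis, chemistry other than ALT, AST, ALP, TBL | Visit 1, then Visit 10 | on feeder treatment | same |
| ALT, AST, ALP, TBL | Visit 3 | after taper to 100 mg BID | effect at 100 mg BID plus any carry-over |
| Vital signs | Visit 3 | same | same |
| mBPI-SF | Visit 3 | same | same |

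If the feeder End of Treatment visit included an ECG or full laboratory panel, the first two rows move to 100 mg BID. They are still on drug.

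**2. How many subjects.** SAP 4.0 gives about 600 subjects, of whom about 250 are De Novo. Rollovers: 600 − 250 = 350, and 350/600 = 58%. The share *s* coming from NKTR-181 is not stated, so I assume 25%, 50% or 75%.

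**3. All-subjects mean change when baseline contains the whole effect.** With a constant effect in everyone, the visible share is 1 − *f*, where *f* = *s* × 350/600.
- *s* = 25%: about 88 subjects, *f* = 0.146, visible share 0.854 (85%)
- *s* = 50%: 175 subjects, *f* = 0.292, visible share 0.708 (71%)
- *s* = 75%: about 263 subjects, *f* = 0.438, visible share 0.562 (56%)

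**4. Visit 3 measures.** The share still visible in an affected subject at dose D is [E(D) − E(100)]/E(D). At 400 mg:
- linear dose-response (assumed): 300/400 = 75%
- Emax with ED50 100 mg (assumed): (0.80 − 0.50)/0.80 = 37.5%
- Emax with ED50 300 mg (assumed): (0.571 − 0.25)/0.571 = 56%

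With *s* = 50%, the combined mean change is 1 − 0.292 × (1 − visible share): 0.93 (linear) and 0.82 to 0.87 (Emax), against 0.71 in step 3. A subject who stays at 100 mg shows none of the effect.

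**5. Pain responders.** If a fraction *r* of pain relief is already present at Visit 3, meeting cut-off *c* needs a total reduction of 1 − (1 − *r*)(1 − *c*) from the pre-drug score.
- *r* = 40%: 1 − 0.6 × 0.7 = 58% for the 30% responder; 1 − 0.6 × 0.5 = 70% for the 50% responder
- *r* = 20%: 1 − 0.8 × 0.7 = 44%; 1 − 0.8 × 0.5 = 60%

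The 40% is the average reduction in the Phase 2 titration period (Protocol 2.3). That study was in knee osteoarthritis and used daily pain scores, so applying it here is an assumption. A Rollover who simply keeps the benefit shows 0% change and counts as a non-responder, in a denominator of all subjects in the analysis set (SAP 8.6.1).

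**6. QTcF change above 30 ms.** Assume a true mean effect of 10 ms and a normal change with SD 15 to 20 ms. With a pre-drug baseline, P(Z > 20/15) = 9% and P(Z > 20/20) = 16%. With a baseline that contains the full effect, P(Z > 30/15) = 2% and P(Z > 30/20) = 7%.

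**The case against.** A reader might infer that changes in all these measures omit the entire drug effect, so that the all-subjects mean always shows only about 71% of it, or 42% (1 − 350/600) if every Rollover came from NKTR-181. The documents do not support that. Visit 3 measures follow a taper to the lowest dose, and escalation to as much as 600 mg BID comes afterwards, so that increment is seen (step 4). The 42% needs no placebo Rollovers, yet Protocol 6.1 and the SAP 8.6 model both provide for them.

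Nor is everything pooled. The mBPI-SF mixed model has De Novo, Rollover from NKTR-181 and Rollover from placebo as separate levels, with a time interaction. The protocol also requires a separate De Novo presentation, so an undiluted estimate will exist. The QTc limits of 450, 480 and 500 ms do not use baseline, and exclusion 15 caps QTcF at entry for all subjects. The Visit 3 reference is legitimate for change since entering this study.

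All of this stands, and it narrows the point without removing it. The mixed model separates the groups but keeps the Visit 3 baseline. The split elsewhere is discretionary, and dose-level tables mix De Novo and Rollover Subjects. Separating the affected group does not restore what its change scores omit.

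Two further limits hold. The feeder schedules are not in these documents, so neither the exact QTcF baseline visit nor the availability of pre-drug values is certain.

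**Conclusion.** The point holds in this form. Every SAP baseline for a Rollover Subject from NKTR-181 is on drug, and the change score omits the effect present at that moment. The loss can be nearly complete for QTcF and the Visit 1 laboratory panel. It is partial for vital signs, the four liver tests and mBPI-SF. De Novo results are not affected.

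The direction follows from the documents; the size rests on assumptions. The 85%, 71% and 56% depend on the assumed share of Rollovers from NKTR-181, on a constant effect, and on placebo Rollovers having an unaffected baseline. They apply only where baseline contains the whole effect. The dose-response shapes, the QTcF effect and SD, and the carrying over of the Phase 2 pain figure are illustrations.

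A reader might also infer that the protocol's QTcF criterion, "has an increase of ≥ 60 msec compared to baseline QTcF", is wrongly set. The documents do not show that. They leave unclear which value is baseline QTcF for a Rollover Subject, and that needs reconciling.

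**What to change.** - **Second baseline.** In SAP 7.2, keep the Visit 3 rule and add for Rollover Subjects the last value before the first NKTR-181 dose in any study, taken from Study 14-181-07 or 14-181-12 where it was collected.
- **Report against both.** Apply both baselines to the change, shift and threshold tables for ECG, laboratory tests and vital signs, and to mBPI-SF change and responder rates.
- **Mandatory split.** Require the split by feeder treatment in all change-from-baseline tables. Label change from Visit 3 in Rollovers from NKTR-181 as change since entering this study (maintenance on treatment).
- **Combined presentation.** Keep the all-subjects summaries that the protocol requires, and show the version with the pre-NKTR-181 baseline alongside.
- **Baseline QTcF.** Reconcile Protocol 1.2 footnote 9, 5.3 and 10.5 with the SAP so that it is clear which value is meant for Rollover Subjects. No clinical rule is proposed.

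The cost is SAP wording, a link to the sponsor's feeder databases (Rollovers keep their subject IDs, Protocol 6.7) and a second set of tables. No new assessments are needed, provided that the feeder studies collected the measures comparably; where they did not, the SAP should say so. The safety changes may look less favourable.
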